#### **4.6. Pre-COVID Era and Post-COVID Era Comparison**

As an additional analysis, the pre-COVID era which will include all Week 100 and Week 104 visits that were planned on or prior to March 1, 2020 will be compared to the same visits that were planned post March 1, 2020.

### TECHNICAL SUMMARY REPORT (TSR)

Name of Sponsor/Company Reata Pharmaceuticals	Individual Study Table Referring to Part of the Dossier: Volume:	(For National Authority Use Only):
Name of Finished Product: bardoxolone methyl capsules	Page:	
Name of Active Ingredient: bardoxolone methyl		
Title of Study: A Phase 2/3 Trial of the Efficacy and Safety of Bardoxolone Methyl in Patients with Alport Syndrome		
Investigators: 
           [name]; [REDACTED]            [name]; [REDACTED]; [name]; [REDACTED]            [name]; [REDACTED]; [name]; [REDACTED]            [name]; [REDACTED]; [name]; [REDACTED]; [name]; [REDACTED]         
		
Study Center(s): Approximately 50 study centers		
Studied period (years): 3.5 years	Phase of development: 3	
Primary and Key Secondary Endpoints:		
Phase 3 – Year 1 Endpoints		
Primary:		

 
• Change from baseline in estimated glomerular filtration rate (eGFR) at Week 48
 
• Safety assessments through Week 52
 
		
Key Secondary:		

 
• Change from baseline in eGFR, following a 4-week drug treatment withdrawal period, at Week 52
 
		
Phase 3 – Year 2 Endpoints		
Primary:		

 
• Change from baseline in eGFR at Week 100
 
• Safety assessments through Week 104
 
		
Key Secondary:		

 
• Change from baseline in eGFR, following a 4-week drug treatment withdrawal period, at Week 104
 
		

**Methodology:**

The Phase 3 portion of the 402-C-1603 trial is a double-blind, randomized, placebo-controlled study designed to evaluate the safety and efficacy of bardoxolone methyl up to 30 mg in patients with Alport syndrome. Patients in Phase 3 are randomized 1:1 to receive bardoxolone methyl or placebo. Randomization is stratified by screening urine albumin to creatinine ratio (ACR). Patients randomized to placebo remain on placebo throughout the study, undergoing sham titration.

Adult patients ( $\geq 18$  years of age) receiving bardoxolone methyl start with once-daily dosing at 5 mg. They dose-escalate to 10 mg at Week 2, to 20 mg at Week 4, and then to 30 mg at Week 6 (only if baseline ACR  $> 300$  mg/g) unless contraindicated clinically and approved by the medical monitor. Patients under the age of 18 receiving bardoxolone methyl start dosing at 5 mg every other day during the first week. They begin once-daily dosing with 5 mg during the second week of the study, and then continue with once-daily dosing following the same aforementioned dose-titration scheme based on baseline ACR at Weeks 2, 4, and 6. Dose de-escalation is permitted during the study if indicated clinically; subsequent dose re-escalation is also permitted to meet the dosing objective of the highest tolerated dose.

All patients receive study drug from Day 1 to Week 48. Patients do not receive study drug treatment during a 4-week withdrawal period (between Weeks 48 and 52). Patients re-start study drug treatment at Week 52 at the same dose level that they received prior to the withdrawal period (maintaining the originally randomized treatment group) and continue study drug treatment through Week 100. A follow-up visit occurs at Week 104 (4 weeks after the last dose). The Data Monitoring Committee (DMC) performs quarterly reviews of unblinded data for safety throughout Phase 3.

The Phase 3, Year 1 efficacy is assessed first by the DMC after all patients in the Phase 3 cohort have completed their Week 52 visit. If the Year 1 efficacy endpoints are met, then the Year 1 data will be analyzed by the Reata analysis team to proceed with regulatory filing. Available Year 2 safety data is summarized descriptively as preliminary results at the time of the Year 1 final analysis. The Phase 3, Year 2 efficacy is analyzed after all patients in the Phase 3 cohort have completed their Week 104 visit.

**Number of Subjects (planned and analyzed):**

Planned: 150

**Diagnosis and main criteria for inclusion (see protocol section 8.1):**

1. Male and female patients  $12 \leq \text{age} \leq 70$  upon study consent;
2. Diagnosis of Alport syndrome by genetic testing (documented mutation in a gene associated with Alport syndrome, including COL4A3, COL4A4, or COL4A5) or histologic assessment using electron microscopy;
3. Screening eGFR (average of Screen A and Screen B eGFR values)  $\geq 30$  and  $\leq 90$  mL/min/1.73 m^2. The two eGFR values collected at Screen A and Screen B visits used to determine eligibility must have a percent difference  $\leq 25\%$ ;
4. Albumin to creatinine ratio (ACR)  $\leq 3500$  mg/g at Screen B visit. Up to 50% of patients in the Phase 2 cohort and approximately 40% of patients enrolled in the Phase 3 cohort can have ACR of 301 to 3500 mg/g. Once enrollment of these patients is complete, the ACR inclusion criterion is  $\leq 300$  mg/g;
5. Patients receiving an angiotensin-converting enzyme (ACE) inhibitor and/or an angiotensin II receptor blocker (ARB) should be receiving the maximally tolerated labeled daily dose (MTLDD), for at least 6 weeks prior to the Screen A visit. The dosage of ACE inhibitor and/or ARB should remain the same throughout the remainder of the study (i.e., no change in dosage or medication), and any potential changes should be discussed with the medical monitor. Patients not currently taking an ACE inhibitor and/or ARB because they are not indicated or because of a medical contraindication may be eligible provided the patient has not taken an ACE inhibitor and/or ARB at least 8 weeks prior to the Screen A visit (these patients must be discussed with the medical monitor prior to enrollment);

**Test product, dose and mode of administration:**

This study uses capsules containing bardoxolone methyl at the 5 and 15 mg strengths. Blinded treatment kits are provided to patients for self-administration orally once daily. Each dose of study drug should be administered at approximately the same time each day, preferably in the morning.

**Duration of study:**

100 weeks of treatment plus a 4-week follow-up

**Reference therapy, dose and mode of administration:**

This study uses matching capsules containing placebo. Blinded treatment kits are provided to patients for self-administration orally once daily. Each dose of study drug should be administered at approximately the same time each day, preferably in the morning.

**Criteria for evaluation (see protocol section 6.2, 11.0):**

*Efficacy:* eGFR, Patient Global Impression of Change (PGIC), Clinical Global Impression-Improvement (CGI-I), the time-to-first kidney failure outcome event defined as the composite endpoint consisting of 30% decline in eGFR, eGFR  $< 15$  mL/min/1.73 m^2, and end stage kidney disease (ESKD) defined as initiation of maintenance dialysis or kidney transplant.

*Safety:* Frequency, intensity, and relationship to study drug of AEs and SAEs, and change from baseline in the following assessments: vital sign measurements, 12-lead ECGs, clinical laboratory measurements, weight, visual acuity, and audiology.

**Statistical methods:**

Primary and secondary analysis of the efficacy data are based on the ITT population, which will include all patients randomized in the Phase 3 portion of the study. Analyses at Weeks 48, 52, 100, and 104 will compare all bardoxolone methyl patients to all placebo patients. Mixed models repeated measures (MMRM) analysis are used to evaluate the treatment effect at Week 48 and 100. ANCOVA is used to evaluate the off-treatment effect at Week 52 and 104. The body of this SAP provides additional detail on analysis of the primary and secondary endpoints, and analyses of exploratory endpoints.

## 1. LIST OF ABBREVIATIONS

**Table 1. List of Abbreviations**

Abbreviation	Term
$\mu_{\text{BARD}}$	bardoxolone methyl group mean
$\mu_{\text{PLACEBO}}$	placebo group mean
ARB	angiotensin II receptor blocker
ACE	angiotensin-converting enzyme
ACEi	angiotensin converting enzyme inhibitor
ACR	urine albumin to creatinine ratio
ACR_STRAT	urine albumin to creatinine ratio use for stratification by the randomization list
AE	adverse event
ALT	alanine aminotransferase
ALP	alkaline phosphatase
ANCOVA	analysis of covariance
AR(1)	first order auto-regressive
ARB	angiotensin II receptor blocker
AST	aspartate aminotransferase
BARD	bardoxolone methyl
BCVA	best-corrected visual acuity
BI	bioinformatics
BMI	body mass index
BNP	B-type natriuretic peptide
BUN	blood urea nitrogen
CGI-I	Clinical Global Impression - Improvement
CI	confidence interval
CKD	chronic kidney disease
CKD-EPI	Chronic Kidney Disease Epidemiology Collaboration
CM	concomitant medication
CRF	Case Report Form
CSR	Clinical Study Report
DMC	Data Monitoring Committee
eCRF	electronic case report form
eDISH	evaluation of Drug-Induced Serious Hepatotoxicity
ECG	electrocardiogram
eGFR	estimated glomerular filtration rate
ESKD	end stage kidney disease
FDA	Food and Drug Administration (US)
FMV	first morning void
GFR	glomerular filtration rate
ICH	International Conference on Harmonisation

Abbreviation	Term
ICH E4	International Conference on Harmonisation Tripartite Guideline for Good Clinical Practice E4
ICH E9	International Conference on Harmonisation Tripartite Guideline for Good Clinical Practice E9
IEC	Independent Ethics Committee
IGF-1	insulin-like growth factor-1
INR	international normalized ratio
IRB	Institutional Review Board
ITT	intent-to-treat
IWRS	Interactive Web Response System
Kg	kilogram
LLD	lower limit of detection
logMAR	log of the minimum angle of resolution
LS	least squares
MAR	missing at random
MedDRA	Medical Dictionary for Regulatory Activities
MMRM	mixed model repeated measures
Msec	milliseconds
MTLDD	maximally tolerated labeled daily dose
NDA	new drug application
NT-Pro BNP	N-Terminal Pro-Brain Natriuretic Peptide
OTAE	off-treatment adverse event
PGIC	Patient Global Impression of Change
pH	potential of hydrogen
PK	pharmacokinetic
PP	per-protocol
PT	preferred term
QTc	corrected QT interval
RBC	red blood cell
RBC/HPF	red blood cells per high power field
SAE	serious adverse event
SAP	statistical analysis plan
SCr	serum creatinine
SD	standard deviation
SOC	system organ class
SOP	Standard Operating Procedure
TBL	total bilirubin
TEAE	treatment-emergent adverse event
TLFs	tables, listings, and figures
ULD	upper limit of detection
ULN	upper limit of normal

Abbreviation	Term
US	United States
WOCBP	women of child-bearing potential
XLAS	X-linked Alport syndrome

## 2. INTRODUCTION

This statistical analysis plan (SAP) describes the planned analyses and data displays to be included in the Clinical Study Report (CSR) for Protocol 402-C-1603 Phase 3.

### 2.1. Trial Rationale

Conceptually, this trial was designed to test the biological hypothesis that bardoxolone methyl slows disease progression in patients with Alport syndrome, as measured by changes in eGFR. Since on-treatment changes in eGFR may include both reversible, pharmacodynamic effects, as well as irreversible structural effects, analysis of eGFR after withdrawal is used to determine if bardoxolone methyl affects disease progression.

The presence of a sustained eGFR improvement after withdrawal of drug may be indicative of disease-modifying activity. In contrast, a decline in kidney function relative to placebo after drug withdrawal would be unlikely to provide a long-term benefit and could indicate the drug has harmed the kidney.

If the withdrawal analysis indicates that bardoxolone methyl improves kidney function relative to placebo, then this would suggest that the drug is likely to reduce underlying progression of the disease. It would also suggest that the on-treatment eGFR change would likely translate into a long-term renal benefit. Further, in routine clinical practice, physicians are unlikely to withdraw the drug, and an important element of the trial is to characterize the on-treatment eGFR change.

Analytically, the main intent of the trial is to characterize the change from baseline in eGFR following a 4-week withdrawal period. Within the two-year duration, there are two opportunities to test this biological hypothesis and determine if the change from baseline in eGFR is statistically significant relative to placebo. If the off-treatment change from baseline in eGFR is not statistically significant relative to placebo at Year 1, the trial design and analysis plan allow for an additional comparison of the off-treatment effect relative to placebo at Year 2.

Beyond the main intent of the trial, the trial is designed to also determine the following:

- The clinical benefit of bardoxolone methyl while receiving treatment, as measured by the on-treatment assessment of eGFR.
- Whether a treatment effect is observed over a period of up to two years.
- Whether a treatment effect trend is seen across various subgroups, such as stages of disease (i.e., across a spectrum of baseline eGFRs) and the pediatric population.

This document describes the analyses of protocol-specified endpoints to assess the effects of bardoxolone methyl on disease progression in patients with Alport syndrome.

### 2.2. Background

The original study protocol has undergone three amendments.

Protocol Revision Chronology:		
Protocol version 1	15-Nov-2016	Original

Amendment 1 (Protocol version 2)	03-Aug-2017	
 
Removed interim analysis for efficacy and potential changes to Phase 3 macroalbuminuria cap
 
Decreased sample size in Phase 3 portion of study
 
Global Impressions of Change added as exploratory endpoints
 

Amendment 2 (Protocol version 3)	30-July-2018	
 
Added time-to-kidney failure as an exploratory endpoint
 
Increased cap on patients with macroalbuminuria in Phase 3
 

Amendment 3 (Protocol version 4)	22-Apr-2019	
 
Re-grouped objectives and endpoints into first and second year objectives and endpoints
 
Modified patient discontinuation and termination criteria
 
Added ESKD follow-up guidance
 

This SAP was developed in accordance with International Conference on Harmonisation Tripartite Guideline for Good Clinical Practice E9 (ICH E9) guidelines. All decisions regarding the final analysis, as defined in this SAP document, were made prior to Database Lock (unblinding) of the study data. Further information can be found in the protocol. Changes to protocol-specified analyses, including analysis populations, can be found in Section 12.

The SAP is based on:

- Protocol No. 402-C-1603, Version 4, dated April 22, 2019
- ICH guidelines E4 and E9 (Statistical Principles for Clinical Trials)
- Feedback received from FDA throughout clinical development, including the following communications:
  - FDA Meeting Minutes [REDACTED] for the October 5, 2016 Pre-IND meeting
  - IND Study May Proceed letter [REDACTED] dated December 15, 2016.
  - Advice/Information Request communication [REDACTED] dated February 5, 2019.

This SAP describes the study populations, how variables are derived, how missing data are handled, and details concerning the statistical methods to be used to analyze the safety and efficacy data from the Phase 3 portion of Study 402-C-1603. Should the SAP and the protocol be inconsistent with respect to the planned analyses, the language of the SAP is governing.

This SAP was finalized, approved by the Sponsor, and placed on file before database lock. This version of the SAP describes the analyses planned prior to the database lock. Unless otherwise specified, the CSR will summarize these analyses. Any substantive changes made to the SAP

after the database lock will clearly be identified in the CSR, and any analyses in addition to those specified in the SAP prior to the database lock are considered ad hoc.

### **3. STUDY ENDPOINTS**

#### **3.1. Study Endpoints**

In patients with Alport syndrome, the study will compare those receiving bardoxolone methyl to those receiving placebo with respect to several endpoints. The timing for analyzing study endpoints is described in Section 5. The strategy for protecting the overall type I error rate of 0.05 for the trial is described in Section 8.4. Primary efficacy analyses are described in Section 8, and additional exploratory efficacy analyses are described in Section 9.

##### **3.1.1. Phase 3 – Year 1 Endpoints**

###### **3.1.1.1. Primary Endpoints**

- Change from baseline in estimated glomerular filtration rate (eGFR) at Week 48
- Safety assessments through Week 52

###### **3.1.1.2. Key Secondary Endpoint**

- Change from baseline in eGFR, following a 4-week drug treatment withdrawal period, at Week 52

###### **3.1.1.3. Exploratory Endpoints**

- Percentage of patients with a kidney failure event by Week 48, defined as the composite endpoint consisting of:
  - 30% decline from baseline in eGFR;
  - eGFR < 15 mL/min/1.73 m^2;
  - ESKD (initiation of maintenance dialysis or kidney transplant).
- Percentage of patients with an increase from baseline in eGFR of 30% or more by Week 48
- Percentage of patients with a decrease from baseline in eGFR of 30% or more by Week 48
- Distribution of changes from baseline in eGFR at Week 48
- Distribution of the Patient Global Impression of Change (PGIC) scores at Week 48
- Distribution of the Clinical Global Impression-Improvement (CGI-I) scores at Week 48

##### **3.1.2. Phase 3 – Year 2 Endpoints**

###### **3.1.2.1. Primary Endpoints**

- Change from baseline in eGFR at Week 100
- Safety assessments through Week 104

### 3.1.2.2. Key Secondary Endpoint

- Change from baseline in eGFR, following a 4-week drug treatment withdrawal period, at Week 104

### 3.1.2.3. Exploratory Endpoints

- Time to first kidney failure composite event, defined as the composite endpoint consisting of:
  - 30% decline from baseline in eGFR;
  - eGFR < 15 mL/min/1.73 m^2;
  - ESKD (initiation of maintenance dialysis or kidney transplant).
- Percentage of patients with a kidney failure event by Week 100, defined as the composite endpoint consisting of:
  - 30% decline from baseline in eGFR;
  - eGFR < 15 mL/min/1.73 m^2;
  - ESKD (initiation of maintenance dialysis or kidney transplant).
- Percentage of patients with an increase from baseline in eGFR of 30% or more by Week 100
- Percentage of patients with a decrease from baseline in eGFR of 30% or more by Week 100
- Distribution of changes from baseline in eGFR at Week 100
- Distribution of the Patient Global Impression of Change (PGIC) scores at Week 100
- Distribution of the Clinical Global Impression-Improvement (CGI-I) scores at Week 100

## 4. STUDY DESIGN

[figure not shown]
### 4.1. Summary of Study Design

The Phase 3 portion of the 402-C-1603 trial is a double-blind, randomized, placebo-controlled study designed to evaluate the safety and efficacy of bardoxolone methyl up to 30 mg in patients with Alport syndrome. Patients in Phase 3 are randomized 1:1 to receive bardoxolone methyl or placebo. Randomization is stratified by screening urine albumin to creatinine ratio (ACR). Patients randomized to placebo remain on placebo throughout the study, undergoing sham titration.

Adult patients ( $\geq 18$  years of age) receiving bardoxolone methyl start with once-daily dosing at 5 mg. They dose-escalate to 10 mg at Week 2, to 20 mg at Week 4, and then to 30 mg at Week 6 (only if baseline ACR  $> 300$  mg/g) unless contraindicated clinically and approved by the medical monitor. Patients under the age of 18 receiving bardoxolone methyl start dosing at 5 mg every other day during the first week; they begin once-daily dosing with 5 mg during the second week of the study, and then continue with once-daily dosing following the same aforementioned dose-titration scheme based on baseline ACR at Weeks 2, 4, and 6. Dose de-escalation is permitted during the study if indicated clinically; subsequent dose re-escalation is also permitted to meet the dosing objective of the highest tolerated dose.

All patients receive study drug from Day 1 to Week 48. Patients do not receive study drug treatment during a 4-week withdrawal period (between Weeks 48 and 52). Patients re-start study drug treatment at Week 52 at the same dose level that they received prior to the withdrawal period (maintaining the originally randomized treatment group) and continue study drug treatment through Week 100. A follow-up visit occurs at Week 104 (4 weeks after the last dose). The Data Monitoring Committee (DMC) performs quarterly reviews of unblinded data for safety throughout Phase 3 and will evaluate the initial Year 1 results as described in Section 8.1.

**Figure 1. Schema for the Phase 3 Portion of the Study**

### 4.2. Definition of Study Drugs

This study uses capsules containing bardoxolone methyl at the 5 and 15 mg strengths, or the corresponding placebos.

### 4.3. Sample Size Considerations

The Year 1 and Year 2 endpoints are not independent hypothesis sets. The endpoints are analyzed using a combination of the Bonferroni and fixed-sequence approaches for type 1 error control (Section 8.4).

The protocol specified enrollment of approximately 150 patients in the Phase 3 cohort. Actual enrollment in the Phase 3 cohort was 157. Sample size calculations for each year based on the actual number of patients enrolled are presented below.

#### 4.3.1. Primary Endpoints

With 157 patients enrolled (78 in one group and 79 in the second group), the study will have approximately 80% power to detect a difference between the two treatment groups in change from baseline in eGFR of 3.4 mL/min/1.73 m^2 for the primary endpoint at Week 48 in Year 1. The power calculation for Year 1, which was based on mixed-model repeated measures (MMRM) analysis, assumes the following:

- 9 repeated measurements (Weeks 1, 2, 4, 6, 8, 12, 24, 36, and 48) having compound symmetry covariance structure
- The correlation between observations on the same subject is 0.7
- Two-sided Type I error rate of 0.025
- Standard deviation of change from baseline in eGFR of 8 mL/min/1.73 m^2
- Analyses at Week 48 are based on the intent-to-treat (ITT) population

Analysis of the Year 2 primary endpoint, which also will use the ITT population, will have approximately 80% power to detect a difference of 3.3 mL/min/1.73 m^2 assuming 13 repeated measurements, a correlation of 0.7 between observations, a standard deviation of 8 mL/min/1.73 m^2, and a two-sided type I error rate of 0.025. The primary analysis of efficacy will use an unstructured covariance structure, which is expected to have approximately the same power as the analysis with compound symmetry used for study planning.

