### **3.2. Clarification of Hierarchical Testing Strategy**

Section 8.4 of the SAP specifies that all endpoints tested at Year 1 and Year 2 will use a significance level of 0.025. Within each year, endpoints are tested following a fixed-sequence hierarchical testing strategy. The total significance level (0.05) was split between Year 1 and Year 2 as a strategy to reserve alpha to test Year 2 if the Year 1 testing sequence was not statistically significant. Formal testing in the sequence may proceed so long as statistically significant evidence of benefit continues to be shown. If in the sequence one endpoint does not show statistically significant evidence of benefit, formal statistical testing of subsequent endpoints will not occur.

As a clarification to the SAP, if there is a significant treatment effect for both Year 1 endpoints, then the significance level for Year 1 (0.025) remains available to be carried forward (recycled or passed along) to the Year 2 testing sequence. Thus, if both Year 1 endpoints are significant, the Year 2 testing sequence will be tested using a significance level of 0.05. This approach aligns with the fixed-sequence method in FDA guidance (Multiple Endpoints in Clinical Trials., January 2017).

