#### 4.3.2. Key Secondary Endpoint

With 157 patients enrolled, the study will have a minimum detectable difference (i.e., 50% power) between the two treatment groups in change from baseline in eGFR of approximately 2.9 mL/min/1.73 m^2, and 80% power to detect a difference of 4.0 mL/min/1.73 m^2 for the key secondary endpoint at Year 1 and at Year 2. The power calculation, which was based on a 2-sample t-test as an estimate for the planned ANCOVA analysis, assumes the following:

- Two-sided Type I error rate of 0.025 for Year 1 and 0.025 for Year 2
- Standard deviation of change from baseline in eGFR of 8 mL/min/1.73 m^2
- Multiple imputation is used for missing data
- Analyses of the key secondary endpoint are based on the ITT population

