### **8.6.1. Primary Analysis of the Year 1 Primary Efficacy Endpoint**

The Year 1 primary endpoint of this study is the change in eGFR at Week 48 (i.e., the end of the first year of drug exposure). The change from baseline eGFR for patients treated with bardoxolone methyl is compared with placebo at Week 48 using mixed models repeated measures (MMRM) analysis, with baseline eGFR (BASE\_eGFR), ACR strata (ACR\_STRAT), and fraction of one-year exposure to treatment (TRT\_EXP1) as covariates and the following fixed factors: treatment group (TRT), time (i.e., VISIT; analysis visit number), the interaction between treatment and time (TRT x VISIT), and the interaction between baseline eGFR and time (BASE\_eGFR x VISIT) as covariates. Inclusion of the fraction of expected one-year exposure to treatment (Section 6.5.11) in the MMRM model as a covariate provides an adjustment for eGFR values collected from early discontinuation patients having less than 1-year of drug exposure.

The trial design separates discontinuation of study drug from discontinuation of study follow-up. Therefore, patients may discontinue early from study drug while continuing follow-up with study visits and assessments. The primary analysis of eGFR at Week 48 uses available eGFR values irrespective of whether or not a patient is receiving treatment. The MMRM analysis uses all eGFR values collected through Week 48 according to analysis visits 0, 1, 2, 4, 6, 8, 12, 24, 36, and 48 (Section 6.5.4). An unstructured covariance matrix is used.

In the event the MMRM model with an unstructured covariance structure does not converge, the following covariance structures are substituted, in the order listed. Each subsequent covariance structure is used only if each previous covariance structure is used and no previous model converged.

1. Heterogeneous Toeplitz covariance structure (assuming different variances at each time point and that measurements taken closer together in time are more highly correlated than those taken farther apart).
2. Toeplitz covariance structure (assuming measurements taken closer together in time are more highly correlated than those taken farther apart).
3. First order auto-regressive [AR(1)] covariance structure (assuming measurements taken closer together in time are more highly correlated than those taken farther apart, but the correlation is more constrained than the Toeplitz structure).

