4. Compound symmetry covariance structure (assuming equal correlation for measurements from a patient, regardless of how far apart in time they were taken). A compound symmetry covariance structure was assumed in the sample size calculation.

The difference between bardoxolone methyl and placebo in change from baseline of eGFR is estimated along with the 95% confidence interval at Week 48 for the primary analysis of the Year 1 primary endpoint.

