### **8.8.1. Primary Analysis of the Year 2 Primary Efficacy Endpoint**

The Year 2 primary endpoint of this study is the change in eGFR at Week 100 (i.e., the end of the second year of exposure). The change from baseline in eGFR for patients treated with bardoxolone methyl is compared with placebo at Week 100 using the statistical model defined in Section 8.6.1 with the following modifications:

- The analysis uses all eGFR values collected through Week 100 according to analysis visits 0, 1, 2, 4, 6, 8, 12, 24, 36, 48, 64, 76, 88, and 100 (Section 6.5.4).
- TRT\_EXP2 is added as a covariate and TRT\_EXP1 is removed.

Inclusion of the fraction of expected two-year exposure to treatment (TRT\_EXP2; Section 6.5.11) in the MMRM model as a covariate provides an adjustment for eGFR values collected from early discontinuation patients having less than 2-years of drug exposure. All eGFR values collected in the Week 52 analysis window assess the effect following 4-weeks of drug withdrawal and therefore are not included in the MMRM analysis of Week 100.

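### SAP 4.3.1 overstates power for the primary endpoints: its inputs give about 66% at 3.4 (Week 48) and 63% at 3.3 (Week 100), not 80%

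*SAP*

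**What the plan says.** SAP 4.3.1 bases its calculation on the 157 patients enrolled, 78 in one arm and 79 in the other. For Year 1 it claims "approximately 80% power to detect a difference between the two treatment groups in change from baseline in eGFR of 3.4" mL/min/1.73 m² at Week 48. The stated assumptions are 9 repeated measurements, compound symmetry, a within-patient correlation of 0.7, an SD of change from baseline of 8, and a two-sided type I error of 0.025. For Year 2 it keeps the correlation, SD and alpha, raises the number of measurements to 13, and claims about "80% power to detect a difference of 3.3". No formula is given, and neither a covariate gain nor missing data is mentioned.

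The analysis sections define the test. In SAP 8.6.1 the MMRM includes treatment, visit and their interaction, and the treatment difference "is estimated along with the 95% confidence interval at Week 48 for the primary analysis" of the Year 1 primary endpoint. In SAP 8.8.1 the change from baseline "is compared with placebo at Week 100 using the statistical model defined in Section 8.6.1", with changes only to the visits used and the exposure covariate. Neither section tests an average over visits.

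Two other places bear on the figure. SAP 4.3.2 takes the same number of patients, SD and alpha for the off-treatment visits, uses a two-sample t-test, and reports "80% power to detect a difference of 4.0". Section 3.2 of the SAP addendum adds that "if both Year 1 endpoints are significant, the Year 2 testing sequence will be tested using a significance level of 0.05".

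**The concern.** Sections 4.3.1 and 4.3.2 share the sample size, SD and alpha, and each concerns a treatment difference at one visit. Yet one finds 3.3 to 3.4 detectable with 80% power and the other 4.0. In Section 4.3.1 the detectable difference also falls as the number of visits rises from 9 to 13. That is how the precision of a visit-averaged difference behaves. A single-visit contrast from a treatment-by-visit model with complete data and compound symmetry does not behave that way.

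Week 48 and Week 100 open their fixed testing sequences (SAP 8.4). Failure at either blocks formal testing of the withdrawal endpoint behind it, and SAP 2.1 calls the withdrawal analysis the main intent of the trial. If power is really in the mid-60s, the chance of missing a true effect of the stated size is about a third, not a fifth. A reader of the study report would then judge a non-significant result against the wrong power.

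**Working it through.** **Inputs (SAP 4.3.1).** n = 78 and 79; SD of change 8; correlation 0.7; compound symmetry; m = 9 (Week 48) or 13 (Week 100); two-sided alpha 0.025. Normal quantiles: 2.2414 for alpha 0.025, 1.9600 for alpha 0.05, 0.8416 for 80% power. √(1/78 + 1/79) = 0.15962. The t-based figures use 155 df.

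**1. Reproducing the stated figures.** For a patient's mean over m visits, SD = 8 × √[(1 + (m − 1) × 0.7)/m].

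| | m = 9 | m = 13 |
|---|---|---|
| SD of visit average | 8 × √(6.6/9) = 6.851 | 8 × √(9.4/13) = 6.803 |
| SE of difference | 1.094 | 1.086 |
| Difference detectable with 80% power, normal (t) | 3.37 (3.40) | 3.35 (3.38) |
| Power at the stated difference, normal (t) | 80.7% at 3.4 (80.0%) | 78.7% at 3.3 (78.0%) |

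The stated figures therefore fit a treatment difference averaged over all post-baseline visits. For Week 100 only the normal formula rounds to 3.3.

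**2. The contrast that is tested.** With complete data and a separate treatment effect at each visit, the estimate at the last visit is the difference in arm means at that visit. Its SE is 8 × 0.15962 = 1.277. A generalised least squares calculation with compound symmetry, correlation 0.7 and treatment-by-visit terms returns 1.277 for both m = 9 and m = 13.

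| | Alpha 0.025, normal (t) | Alpha 0.05, normal (t) |
|---|---|---|
| Detectable with 80% power | (2.2414 + 0.8416) × 1.277 = 3.94 (3.97) | (1.9600 + 0.8416) × 1.277 = 3.58 (3.60) |
| Week 48, power at 3.4 | Φ(3.4/1.277 − 2.2414) = 66.3% (65.5%) | does not apply |
| Week 100, power at 3.3 | Φ(3.3/1.277 − 2.2414) = 63.4% (62.6%) | Φ(3.3/1.277 − 1.9600) = 73.4% (72.8%) |

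The alpha 0.05 column applies to Year 2 only, and only if both Year 1 endpoints are significant (addendum 3.2).

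**3. Cross-check with SAP 4.3.2.** By t-test with SD 8 and alpha 0.025, power is 80.7% at 4.0 and 50.4% at 2.9. Both match that section's stated 80% and 50%.

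**4. Covariate gain needed to rescue the claim at alpha 0.025.** The residual SD would have to be 3.4/(3.083 × 0.15962) = 6.91 at Week 48 and 3.3/(3.083 × 0.15962) = 6.71 at Week 100 (6.85 and 6.65 by t). Covariates would have to explain 1 − (6.91/8)² = 25% and 1 − (6.71/8)² = 30% of the variance of change (27% and 31% by t).

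**5. Two assumed baseline adjustments.** The SAP gives no correlation with baseline, so 0.7 is borrowed here as an assumption.

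- *Single-measurement baseline.* The variance of change is 0.6σ² = 64 and the residual variance is 0.51σ², so the residual SD is 7.38.
- *Weighted baseline of SAP 6.4.1* (half Day 1, a quarter each for two screening values). The baseline variance is (0.3 × 0.375 + 0.7)σ² = 0.8125σ². The variance of change is (1 + 0.8125 − 1.4)σ² = 0.4125σ² = 64. The residual variance is (1 − 0.49/0.8125)σ², so the residual SD is 7.85.

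| Residual SD | Week 48 at 3.4, alpha 0.025 | Week 100 at 3.3, alpha 0.025 | Week 100 at 3.3, alpha 0.05 |
|---|---|---|---|
| 7.38 | 74.1% | 71.3% | 80.0% |
| 7.85 | 68.2% | 65.3% | 75.0% |

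Neither reaches 80% at the stated alpha.

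**The case against.** The strongest objection is that 66% and 63% take 8 as the residual SD. The planned model adjusts for baseline eGFR, its interaction with visit, ACR stratum and exposure fraction, and Section 4.3.1 does not say whether 8 is before or after adjustment. This stands in part, because the size of the shortfall depends on the gain. But the section calls 8 the SD of change and credits no reduction. The two adjustments tried give 68% to 74% at Week 48 and 65% to 71% at Week 100 at alpha 0.025. The one case that reaches 80% (Week 100) needs both an unstated covariate gain and the conditional alpha of 0.05.

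A second point is that the sponsor's formula is not shown, so averaging over visits is an inference from fit, and the fit for 3.3 is loose. That is fair. It concerns how the figure arose, not whether it describes the test. The arithmetic may well be sound for a different quantity, so this is better called a mismatch between the planning calculation and the tested contrast than a slip.

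Third, with missing data the earlier visits do recover information. True, but not beyond complete-data precision. If 20% of patients missed only the last visit (an assumption), the SE would be 1.43 from that visit alone and 1.33 with nine visits, still above 1.277. Nor does the SAP's remark that unstructured covariance gives about the same power help, since the shortfall comes from the contrast.

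Fourth, SAP 12.1 expects off-treatment values to differ in variability, and it openly reports that moving from MMRM to a t-test raised the 50%-power difference from 2.2 to 2.9. Yet Section 4.3.2 still assumes an SD of 8, so the comparison with 4.0 is like for like on the stated inputs.

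Finally, enrolment is complete, and a null result would be read mainly from its estimate and interval. That limits the consequence but leaves the statement wrong.

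**Conclusion.** The concern holds. On the inputs in Section 4.3.1, power for the contrasts tested is about 66% at 3.4 (Week 48) and 63% at 3.3 (Week 100) at two-sided alpha 0.025. The chance of missing a true effect of that size is about 34% and 37%, against the implied 20%. If the Year 2 alpha is 0.05, power at Week 100 is about 73% and the miss probability about 27%.

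These figures assume complete data and an SD of 8 at the tested visit, with no covariate gain. Missing data would lower power. A covariate gain would raise it, but would have to explain 25% to 31% of the variance of change to restore 80% at alpha 0.025. Type I error, the testing sequence and the validity of the analysis are not affected. The statement should be corrected, but the point does not threaten the trial.

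**What to change.** Restate SAP 4.3.1 as follows:

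- With 157 patients, SD 8 and two-sided alpha 0.025, power is about 80% for a difference of about 4.0 at Week 48 and at Week 100. It is about 66% at 3.4 and about 63% at 3.3.
- Remove the dependence of the detectable difference on 9 or 13 visits. If the calculation is instead meant to allow for missing data, where earlier visits do help, state the assumed missingness and covariance.
- For Year 2, add that if both Year 1 endpoints are significant and alpha is 0.05, the detectable difference is about 3.6 and power at 3.3 is about 73%.
- If a gain from covariate adjustment is claimed, give the assumed residual SD and its basis.

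The cost is a few sentences of SAP text. No patients are added, and no test, alpha level or population changes. The only downside is a less favourable stated figure, which would then agree with Section 4.3.2.
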